## 2 OBJECTIVES AND ENDPOINTS

### 2.1 Study Objectives

The **primary objective** of the study is to compare

- The quality of high-performance Ethos CBCT images (acquired with breath hold and under free breathing) with that of fan-beam CT (CT simulation) acquired with breath hold, where the latter represents a best-case benchmark; and
- The quality of high performance Ethos CBCT images (acquired with breath hold and under free breathing) with that of Truebeam CBCT acquired with breath hold, where the latter represents the status-quo for image guidance.

The **secondary objectives** of the study are:

1. To compare treatment dosimetry calculated on the Ethos CBCT images to that calculated on both the fan-beam CT and the Truebeam CBCT.
2. To compare the patient experience of CBCT image acquisition between the Ethos CBCT and the existing Truebeam CBCT.

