#### 2.2.2 Secondary Objective Metrics

Dose-volume histograms for key target structures and organs at risk will be calculated from the Ethos and TrueBeam CBCT images and compared to those from the existing dosimetric plan for each patient to determine the accuracy of the dosimetric calculations based on the CBCTs.

The patient experience with CBCT image acquisition will be determined through the use of a questionnaire comparing the TrueBeam CBCT image acquisition process to that of the Ethos CBCT process.

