3. Anonymized fan-beam CT images, status-quo CBCT image and Ethos CBCT image data sets (with breath hold and with free breathing) will be presented to multiple observers for qualitative assessment of perceived image quality. Observers will include up to five radiation oncologists and five radiation therapists, who will answer questions on image quality for contouring and image guidance purposes, respectively. Image quality will be scored either as a simple ranking (1 to 3) or using a five-point Likert scale. This review will be done using the MeVis framework (see example, Figure 2) that allows centralized user management and authentication, ensuring controlled access to data with unique login credentials for each individual. In the case of Likert scale ranking, analysis will be performed using a Mann-Whitney test.

[figure not shown]

Figure 2 Example of qualitative image review using the MeVis framework.

4. A patient experience questionnaire will be provided to each subject on the day they undergo CBCT imaging on the Ethos platform. Subjects will be encouraged to fill out the questionnaire on that day. Study coordinators will transcribe subject responses into the study database.

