## 10 STATISTICAL CONSIDERATIONS

### 10.1 Sample Size

The study design does not involve any intervention in the subject's cancer care. The study is being performed to assess the image quality in a new CBCT system.

This study will accrue thirty (30) subjects, which will include:

- A minimum of 7 subjects with liver cancer
- A minimum of 7 subjects with lung cancer
- A minimum of 7 subjects with cancer in the left breast

Subjects with other cancers can be included so long as the patients meet the study's inclusion/exclusion criteria.

Seven subjects in each cohort will provide sufficient image data for a range of subject variation in the same anatomical site.

Data will be collected and analyzed as described in Section 5. Quantitative image quality metrics for the different imaging modalities will be compared using average values and standard deviations. Qualitative evaluations of image quality using a Likert scale will be compared using a Mann-Whitney test. Dosimetry will be compared using average values of metrics derived from dose-volume histograms and standard deviations of those values. Patient experience of the different CBCT acquisitions will be compared qualitatively based on responses to questionnaires.

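### Patient experience is a comparative secondary objective observed within subjects, but the planned qualitative comparison gives no estimate or interval

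*Combined protocol and SAP*

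**What the plan says.** Section 2.1 lists as its second secondary objective: "To compare the patient experience of CBCT image acquisition between the Ethos CBCT and the existing Truebeam CBCT". The synopsis gives the same aim, setting the fast single-breath-hold acquisition against the slower standard one. Section 2.2.2 names the instrument as "a questionnaire comparing the TrueBeam CBCT image acquisition process to that of the Ethos CBCT process".

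Section 5.2 says when it is given: "A patient experience questionnaire will be provided to each subject on the day they undergo CBCT imaging on the Ethos platform". On completion it says: "Subjects will be encouraged to fill out the questionnaire on that day". Coordinators then transcribe the answers into the study database. Under section 3.1, a subject's participation is complete only when the study scans and the questionnaire are both done.

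The analysis is one sentence in section 10.1: "Patient experience of the different CBCT acquisitions will be compared qualitatively based on responses to questionnaires". In the same paragraph, the image metrics and the dosimetry receive means and standard deviations, and the observers' Likert scores receive a Mann-Whitney test.

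The sample size is stated as "This study will accrue thirty (30) subjects". Its justification concerns images only: "Seven subjects in each cohort will provide sufficient image data for a range of subject variation in the same anatomical site". The questionnaire's items, response scale and scoring are not described.

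**The concern.** Section 1.1 names a better patient experience, alongside better image quality, as an expected result of the faster scan. A reader will therefore look for the size of any preference and its uncertainty. Of the outcomes in the section 10.1 paragraph, patient experience is the only one with neither a numerical summary nor a test.

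The data are naturally paired, because the same person undergoes both acquisitions. A within-subject estimate needs no extra subjects, visits or scans. Without one, a report that most patients preferred Ethos could rest on a result compatible with an even split or on a clear majority, and the planned analysis would not tell the reader which.

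**Working it through.** **The plan's own figure.** There is nothing to reproduce. The 30 subjects (at least 7 each with liver, lung and left breast cancer; 7 + 7 + 7 = 21, which fits within 30) are not tied to any effect size, standard deviation, power or precision target.

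**Inputs.** n = 30 comes from section 10.1. The rest is assumed: the counts preferring Ethos are illustrative, every subject answers, and every answer names one machine (no ties).

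**Formula.** Exact (Clopper-Pearson) 95% interval for x out of n:

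- lower limit = 2.5% quantile of Beta(x, n − x + 1)
- upper limit = 97.5% quantile of Beta(x + 1, n − x)

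| Preferring Ethos | Share | Exact 95% CI |
|---|---|---|
| 18/30 | 60% | 40.6% to 77.3% |
| 20/30 | 67% | 47.2% to 82.7% |
| 21/30 | 70% | 50.6% to 85.3% |
| 22/30 | 73% | 54.1% to 87.7% |
| 24/30 | 80% | 61.4% to 92.3% |

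All five rows could be summarised in words as most patients preferring Ethos. The first two include 50%; the last three do not. At 20/30 the half-width is (82.7 − 47.2)/2, or about 18 percentage points.

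**Non-response.** No completion rate is given. With an assumed 20 usable answers, 14/20 (70%) has an interval of 45.7% to 88.1%. The same 70% that excludes an even split with 30 answers does not exclude it with 20.

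**Ties.** A preference item should allow a no-difference answer, and then the denominator matters. Suppose 14 prefer Ethos, 6 prefer TrueBeam and 10 see no difference (14 + 6 + 10 = 30).

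- Among all respondents: 14/30 = 47%, interval 28.3% to 65.7%.
- Among those stating a preference: 14/20 = 70%, interval 45.7% to 88.1%.

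Both are legitimate summaries of the same data, but 50% is the even-split reference only for the second. This is why all three counts and both proportions are needed.

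**What the design could support.** Take an exact two-sided sign test at an assumed 5% level, with 30 stated preferences. It needs at least 21 of 30 for one machine (attained level 4.28%). Its power is 18%, 59%, 80% and 94% at true preference shares of 60%, 70%, 75% and 80%. These figures only gauge the information available; they are not an argument for adding a test.

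**The case against.** The strongest case against is proportionality. This is the second of two secondary objectives in a single-site feasibility study that states no hypothesis, alpha or success criterion. The primary image metrics and the dosimetry get only means and standard deviations. Descriptive reporting is acceptable here, and demanding a test would hold this outcome to a stricter standard than the primary one. That stands, and it is why the request stops at an exploratory estimate with an interval. It does not defend having no numerical summary at all.

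Second, the protocol uses the word qualitative loosely: section 10.1 applies it to Likert scores that are then tested. The sentence on patient experience may therefore permit tabulated counts. A reader might infer a narrative written by staff who know the hypothesis, but the documents say neither that the summary is a narrative nor who writes it. What remains is that the sentence commits to no count, estimate or interval.

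Third, a reader might infer that all 30 subjects rate each machine separately. Section 2.2.2 confirms only a questionnaire comparing the two processes, and same-day completion is merely encouraged. If closed items do not exist, no paired estimate can be drawn from the responses. This stands, so the change must reach the items as well as the analysis sentence.

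Fourth, an interval deals with chance only. Subjects know which machine they are on, and section 5.1 allows Ethos imaging either before or after a treatment fraction with no control of order. That also stands and should be stated with the result.

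**Conclusion.** The point holds as a gap in the planned analysis. Secondary objective 2 is comparative and within-subject, and the plan names no estimate or interval for it. At 30 responses without ties, majorities of 60% to 67% are compatible with an even split while 70% or more is not, and a qualitative comparison as stated would not separate the two.

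A reader might go further and infer that the trial itself cannot tell a real preference from chance. The documents do not support that. The responses are stored in the database, and if the items are closed, 30 paired answers would give useful information about a large preference.

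The figures rest on assumed counts, full response and no ties. Non-response would widen the intervals, and no-difference answers would change the figures according to the denominator used. Given the feasibility setting, this is a cheap improvement and not a threat to the study.

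**What to change.** **Questionnaire.** Include one overall preference item (Ethos / TrueBeam / no difference). If not already so, word closed items in parallel for each system on one ordered scale. State whether the Ethos answers refer to the breath-hold scan, the free-breathing scan or both, since each subject has both.

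**Section 10.1.** State that the report will give:

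- the number of completed questionnaires;
- the counts in all three preference categories;
- the proportion preferring Ethos with an exact 95% CI, with no-difference answers kept in the denominator and also among those stating a preference;
- the within-subject score difference with a 95% CI by a paired method, for example the Hodges-Lehmann estimate with its signed-rank interval. The Mann-Whitney procedure used for the observer scores would ignore the pairing.

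Label the analysis exploratory, require no significance test, and keep free-text answers qualitative. Add that the interval addresses chance only, not bias from unblinded ratings or uncontrolled scan order.

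**Cost.** A few sentences in section 10.1, a check of the item wording, and possibly one extra item for the subject. No extra subjects, visits or scans.
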